1 STUDY SUMMARY

1.1 Synopsis

Title:	Open label comparison of injectable extended release buprenorphine (CAM2038, Brixadi®) and naltrexone (Vivitrol®) for the treatment of opioid use disorder
Short Title:	Brixadi and Vivitrol
Study Description:	
This study will elucidate the cognitive mechanisms of response to opioid agonists and antagonists used to prevent relapse in OUD through investigation of the underlying neural circuits. We shall use previously validated cognitive probes, functional Magnetic Resonance Imaging (fMRI), and extended-release injectable preparations of opioid partial agonist buprenorphine (XR-BUP, Brixadi) and opioid antagonist naltrexone (XR-NTX, Vivitrol), in OUD patients. Using two medications with opposing mu opioid receptor action will allow a comprehensive evaluation of the mechanisms of response to relapse prevention pharmacotherapy in OUD. The study will determine the presence of treatment effects in the domains of executive function, incentive salience, and resting functional connectivity and the interaction that will indicate a difference between the two medications. Then we will evaluate the ability of the brain fMRI signal to explain relapse defined by % of opioid-positive urine tests and adherence to the study interventions. Participants will be recently detoxified treatment-seeking patients with OUD who will receive 3 monthly injections of XR-NTX or XR-BUP and have weekly urine toxicology monitoring. The project will enroll 200 participants over 6 years. The proposal would be the first neural systems' level investigation of the cognitive effects of the next generation extended release preparation of buprenorphine and naltrexone to explain the individual heterogeneity of OUD treatment response and failure. This project has the potential to advance the theory and personalized treatment of OUD by elucidating the brain mechanisms of vulnerability to relapse in OUD and in SUD in general.
 
The proposal is similar to an existing UPenn IRB protocol 814234 and Biomarkers of disease and response to treatment in opioid addiction in all aspects except the addition of XR-BUP, Brixadi.

Objectives:	Compare brain fMRI response to injectable extended-release buprenorphine (Brixadi, XR-BUP) and naltrexone (XR-NTX, Vivitrol)

**Medications
and
Interventions**

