XRBUP (CAM2038, Brixadi) is a subcutaneous (SC) injectable extended-release formulation of buprenorphine that has been developed by Camurus AB (Sweden) and licensed in the US by Braeburn Pharmaceuticals. Brixadi is available in a range of weekly and monthly doses (8,16,24 and 32 mg weekly and 64 and 96 mg monthly) (Lofwall et al 2018). CAM2038 was approved under brand name Buvidal for OUD by the European Medicines Agency and approved as Brixadi by the FDA. This creates a unique window of opportunity for research. Braeburn, the US licensee of Brixadi has agreed to provide the study medication at no cost (See Letter of support).

XRNTX (Vivitrol): is a monthly extended-release intramuscular injection of 380 mg of naltrexone manufactured by Alkermes Inc, that has been approved by the FDA for OUD since 2010 (Lee et al 2017) XRNTX maintains therapeutic levels of naltrexone and its active metabolites for approximately 4 weeks after each injection.

Functional magnetic resonance imaging (fMRI): is an established method of clinical medical imaging. Combined with **neurocognitive testing**, standard clinical MRI scanner can be used as an accurate and robust means of evaluation of brain response to medications such as opioid agonists and antagonists, that modulate cognitive and motivational processes in addiction (Davis et al 2017, Moningka et al 2019).

Neurocognitive testing: Psychological tasks are a well-established means to evaluate a particular cognitive or emotional domain. We shall use established tasks probing four domains: motivation, response inhibition, emotional controls and awake rest during the fMRI sessions, to simultaneously assess domain-specific behavioral performance and brain activity.

Group (XRNTX, XRBUP) by Session (PRE, ON) **interaction** in the brain fMRI signal in 4 cognitive domains

**Primary
Endpoint:**

Domain-specific cognitive performance, Urine toxicology, Adherence to follow up and treatment visits.

**Secondary
Endpoints:**

**Study
Population:**

200 individuals between the ages of 18 and 65 who have a diagnosis of Opioid Use Disorder (OUD).

Phase:

Phase 2a/b

**Description of
Sites/Facilities**

UPenn Department of Psychiatry, Center for the Study of Addictions, [name]

**Enrolling
Participants:**

UPenn Center for the Study of Addictions

Description of Study Intervention: XRBUP (CAM2038) or XRNTX (Vivitrol)

Study Duration: Six years (72 months)

Participant Duration: 20 weeks

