- 3) Participants who successfully complete detoxification, will undergo a neuroimaging session immediately followed by induction to XRNTX or XRBUP over a period of up to 14 days, which will include oral Naltrexone 50 mg for the XRNTX group followed by the 1st injection of XRNTX, or by injection of one or more weekly XRBUP in 8mg, 16mg or 24 mg strength with the total weekly dose not to exceed 32mg, followed by an injection of monthly XRBUP in 64, mg, 96mg, or 128mg strength (**Figure 1**). If deemed clinically necessary, induction to XRBUP may be extended by up to one week, using the same weekly Bixadi schedule. Buprenorphine/naloxone (Suboxone) is an FDA-approved sublingual form of buprenorphine that may be used during the induction if clinically indicated. Total duration of induction onto XRBUP will not exceed 14 days. Participants who are unable to complete the detoxification or induction will be excluded from the study and referred to a clinical addiction program for continuation of treatment as indicated. Suspected adverse reactions to any of the medications used in the study will be reported appropriately to the IRB, FDA at [name] or www.fda.gov/medwatch, Alkermes, plc at [name] or email: [contact] or both or Braeburn Inc at [name] .

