3.1 General Design

Study Design: The proposed study is a prospective open label 2-group study to compare the brain and behavioral responses of individuals with OUD receiving XRBUP and XRNTX treatments. The study will be conducted in two phases – Phase 1 = feasibility and Phase 2 = confirmation. Study interventions (XRNTX and XRBUP) and their duration will be same in both phases. Phase 1 (2 years) will have more cognitive and behavioral probes, some of which may not survive into Phase 2 (3 years) if found to not yield significant discrimination between the study interventions (groups). Participants will be men and women with current DSM-5 diagnoses of opioid use disorder (OUD) who will be randomized to XRBUP or XRNTX. Phase 1 will recruit 60 participants and Phase 2 will recruit 200 participants. The study length for each participant is comprised of up to 30 days of screening and baseline evaluations (called “week 1”), a 12-week open label trial (medication phase), and one follow-up visit 4 weeks after end of medication phase. The overall duration of the project will be 5 years (60 months). We intend to recruit 4 subjects per month for 40 months.

Table 1. Study timeline

Year/Phase	Year 1 (Phase 1)				Year 2 (Phase 1)				Year 3 (Phase 2)				Year 4 (Phase 2)				Year 5 (Phase 2)			
Quarter	Q1	Q2	Q3	Q4																
Preparation	X	X	X	X					X	X										
Recruitment		X	X	X	X	X	X	X	X	X	X	X	X	X	X	X	X			
Data Collection		X	X	X	X	X	X	X	X	X	X	X	X	X	X	X	X			
Data Analysis/QC			X	X	X	X	X	X	X	X	X	X	X	X	X	X	X	X	X	X
Publication				X	X			X	X			X	X			X	X	X	X	X

Figure 1: Outline of study interventions

3.2 Primary Study Endpoints (see Table in the Schedule of Activities (SoA), [Appendix Section 12.1](#)).

Clinical:

- 1) percent of the urine drug screen (UDS) tests positive for opioids during the last month of participation.
- 2) The number of study interventions (1,2 or 3) participant adhered to.

Surrogate: Brain fMRI response in three cognitive domains:

- 1) Response inhibition (Go-NoGo task)
- 2) Drug cue reactivity (Opioid Cues task)
- 3) Emotional identification (IDemo Task)
- 4)

Primary Hypothesis:

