4.4 End of Study Definition

A participant is considered to have completed the study if he or she has completed all phases of the study including the last visit or the last scheduled procedure shown in the Schedule of Activities (SoA), [Appendix Section 12.1](#). Proper referral and continuation of treatment after study discontinuation, with an option to continue the same medication for Vivitrol group and options to switch to oral preparation of buprenorphine or a biosimilar injectable extended release preparation that is available on the US market.. Participants will be offered referrals commensurate with their treatment preferences and the medication they received in the study. Individuals who drop out of study pharmacotherapy will be offered to continue their follow up visits. Individuals who drop out of study pharmacotherapy will be offered to continue their follow up visits. Participants completing the study will be referred to the clinical program of their choice using a “warm-handoff” procedure that will include (1) beginning to make arrangements for post-study referral before the effects of XRNTX or XRBUP wear off allowing one month for the project coordinator and the participant to establish clinical treatment (2) monitoring and assisting participants in making their follow up appointment and escorting them to their first appointment as needed (3) Providing psycho-education about opioid overdose risk and provide prescriptions for the nasal Naloxone spray used as a rescue in case of an overdose.

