The clinical management of XRBUP is similar to XRNTX except that induction to XRBUP requires partial detoxification followed a weekly dose of injectable XRBUP, while induction on XRNTX requires complete abstinence (Lofwall et al 2018). The goal of the detoxification and induction phase of the experiment is to establish a uniform starting point for both monthly formulations. To achieve it, we will detoxify all participants to abstinence and randomize after abstinence from illicit opioids has been achieved. Outpatient detoxification to abstinence takes between 5 and 10 days. Following detoxification, the XRBUP participants will receive a combination of 8mg, 16mg, and 24mg strengths of weekly XRBUP, not to exceed 32 mg/week, followed by the injection of 64mg, 96mg, or 128mg of monthly XRBUP. If clinically indicated, supplemental doses of sublingual buropenorphine/naloxone (Suboxone) may be used. If clinically indicated, the induction procedure may be extended by up to one week, using the same approach. The total duration of induction to Brixadi will not exceed 14 days. The XRNTX participants will receive 50 mg of oral naltrexone for 7-10 days after detoxification followed by the 1st XRNTX (380 mg naltrexone IM) injection. The use of symptom-driven titration of weekly XRBUP during induction reflects current best practices in administration of the drug and increases participant safety and comfort. The XRBUP induction period is also intended to synchronize the timepoint at which both cohorts begin their monthly treatments. The non-opioid detoxification will follow the procedure described in our previous neuroimaging studies (Langleben et al 2014, Langleben 2015, Wang et al 2018). Participants who are opioid-positive upon screening will undergo office-based withdrawal management (detox) by the study physicians using FDA-approved generic medications to alleviate opioid withdrawal symptoms following a symptom-triggered approach that includes clonidine 0.1 mg tid, dicyclomine 20 mg qid, clonazepam 0.5 mg q12 hrs PRN, diphenhydramine 25 mg PRN, non-steroidal anti-inflammatory medicines PRN, Trazodone 50 mg qhs and oral hydration solutions (Molenberghs et al 2005). The induction to XRNTX or XRBUP will commence immediately after the baseline MRI session. The 1st monthly injection will be administered by an experienced nurse practitioner after induction is completed (approximately 7-14 days later).

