Missing Data and Nonadherence: For the longitudinal analyses described above, premature discontinuation from treatment and occasional missing daily use indicators will lead to incomplete data. The mixed effects models described above can make use of all available data provided by subjects, but the inferences drawn from them will be unaffected by the missing data only if the missing data can be regarded as ignorable, in the sense of Laird ⁵⁵. To assess the sensitivity of our analyses to this assumption, we will use shared parameter models, which allow for correlated random effects underlying the cocaine use measurements and the pattern of dropout ⁵⁶. We will also use selection models to examine the effects of missing data ^{57,58}. We will explicitly model the probability of premature discontinuation at a time point as a function of baseline characteristics and responses at previous time points, using a logistic regression model, and incorporate the predicted probabilities into a weighted analysis of the main hypotheses. We will do analyses in a range of assumptions and assess the sensitivity of results to them ⁵⁸. We will use urine drug screens, record of clinic visits and receipt of injectable medications as measures of compliance with assigned medication regime. We will use the methods of Nagelkerke et al ⁵⁹ and Small et al ⁶⁰, to obtain estimates of the intervention effect in a population compliant with treatment i.e. the Complier Average Causal Effect (CACE).

Safety: The adverse event responses will be analyzed as a measure of safety. Total number of adverse events, adverse events leading to discontinuation (in the judgment of the study physician), % of patients reporting at least one adverse event, clinical lab assessments, vital signs and

evidence of clinical worsening (by urine drug screen results and TLFB results) will be considered in assessment of safety. In a manner parallel to the analysis for therapeutic response, medication group, gender, age and other clinical variables will be entered into a generalized linear mixed effects model to predict adverse events.

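### The primary adherence count in section 3.2 runs from 1 to 3, so it has no value for a participant who is randomised but gets no monthly injection, and the synopsis gives adherence a different measure and tier

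*Combined protocol and SAP*

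**What the plan says.** **The count.** Section 3.2 puts "The number of study interventions (1,2 or 3) participant adhered to" among the primary clinical endpoints.

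**The synopsis (1.1).** Its secondary endpoints are "Domain-specific cognitive performance, Urine toxicology, Adherence to follow up and treatment visits". Its study description speaks instead of "relapse defined by % of opioid-positive urine tests and adherence to the study interventions".

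**Section 9.4.1.** It combines several sources: "We will use urine drug screens, record of clinic visits and receipt of injectable medications as measures of compliance with assigned medication regime".

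**Order of events.** Under the detoxification and induction text of section 6.1, the plan is to "randomize after abstinence from illicit opioids has been achieved". Induction follows: oral naltrexone in one arm, weekly XRBUP in the other. The first monthly injection comes after induction, about 7 to 14 days later. The schedule in 13.1 also places randomisation before induction.

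**Participants who do not reach the first monthly injection.** Section 2.3.1 says "Participants who are unable to complete the detoxification or induction will be excluded from the study". Section 7.2 allows replacement of participants who were randomised but not injected. Section 9.3 defines the all-treated population as anyone randomised who had at least one dose of study drug. Section 9.1 counts refusal of medication or dropout as treatment failure in the binary composite.

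**The concern.** A randomised participant who leaves during induction, or does not return for the first monthly injection, has received none. On this measure that is the lowest possible adherence, and the section 3.2 scale has no number for it. If such people are left out, the endpoint is conditional on an event after randomisation, reached by a different induction path in each arm. The comparison is then no longer between the groups as randomised, and an arm that loses more people in induction is not marked down for it.

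The second difficulty is that the plan does not settle what adherence is or where it ranks. It is a primary count of interventions in 3.2 and a secondary measure of visits in the synopsis list. The two can diverge, because section 4.4 says "Individuals who drop out of study pharmacotherapy will be offered to continue their follow up visits". A person who stops injections but keeps attending may score well on visits and poorly on injections.

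**Working it through.** **1. Can a count of 0 occur?** Yes. Sections 6.1 and 13.1 place randomisation before induction, and section 7.2 provides for participants who are randomised and not injected.

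**2. Can such a person be in the analysis set?** Yes, in at least one arm. Weekly XRBUP is part of the investigational agent as section 6 describes it. A participant given a weekly dose who then leaves has had study drug and meets the section 9.3 definition, but has no permitted count. In the other arm induction is oral naltrexone, and the plan does not say whether that is study drug. The same kind of induction failure may be inside the set in one arm and outside it in the other.

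**3. How many people?** Section 5.3 expects about 75% of 200 recruits, stated as 160, to reach the first monthly injection. These do not match: 200 × 0.75 = 150, and 160/200 = 80%. So 40 to 50 of 200 recruits get no monthly injection. This is only an upper bound for the randomised, because section 5.3 ties the loss to achieving abstinence and section 6.1 randomises after abstinence. No split is given.

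**4. What does the missing 0 do?** The inputs are assumptions, except that 70 per arm is the section 9.1 figure, used here as the number randomised. Among those with at least one monthly injection, take proportions with 1, 2 and 3 injections of 0.20, 0.20, 0.60 (XRNTX) and 0.125, 0.125, 0.75 (XRBUP). Section 4.1 cites 50% to 75% retention at the third XRNTX injection and about 75% at three months on sublingual buprenorphine.

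- XRNTX: mean 0.20×1 + 0.20×2 + 0.60×3 = 2.40; variance 6.40 − 2.40² = 0.64.
- XRBUP: mean 0.125×1 + 0.125×2 + 0.75×3 = 2.625; variance 7.375 − 2.625² = 0.484.
- With a share f scored 0: mean m(1−f); variance (1−f)(v + m²) − m²(1−f)².
- Power (two-sided 5%, normal approximation): Φ(|difference|/SE − 1.96) plus the negligible opposite tail. The 1-to-3 count uses 70(1−f) per arm; the count with 0 uses 70.

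| Induction loss XRNTX / XRBUP | Difference (XRBUP − XRNTX), 1–3 | Difference, 0–3 | Power, 1–3 | Power, 0–3 |
|---|---|---|---|---|
| 5% / 5% | 0.225 | 0.21 | 41% | 28% |
| 15% / 5% | 0.225 | 0.45 | 39% | 75% |
| 25% / 5% | 0.225 | 0.69 | 36% | 97% |
| 5% / 15% | 0.225 | −0.05 | 39% | 6% |

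For 5%/5%: the 1-to-3 SE is √((0.64 + 0.484)/66.5) = 0.130 and 0.225/0.130 = 1.73. With 0, the variances are 0.882 and 0.788, the SE is √(1.670/70) = 0.154, and 0.214/0.154 = 1.38.

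The 1-to-3 difference never moves. The count with 0 follows the loss in either direction.

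**5. Top of the scale.** The synopsis and 13.1 have three monthly injections. Section 4.1 refers to two, and section 6.4 lists observed injections on days 10 and 40 only. The maximum count is therefore inconsistent too.

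**The case against.** Five points can be made for the plan.

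- **The plan does score these people elsewhere.** A reader might infer that the worst adherers cannot be scored at all. The documents do not support that: the section 9.1 composite, the clinical outcome that section 9 models, counts refusal and dropout as failure. This stands and confines the point to the count.
- **No planned test is affected.** Section 9 names no between-arm analysis of the count. This also stands; the differences and power above describe a comparison the plan does not specify. But 3.2 calls the count a primary clinical endpoint, so it will be reported.
- **The count may be meant as conditional on a first injection, or the figures in brackets may only number the injections.** Either is possible and 3.2 states neither. Exclusion in 2.3.1 and replacement in 7.2 do not resolve it, because both can act after randomisation.
- **Two endpoints, not one defined twice.** A reader might conclude that the same endpoint has two contradictory scores. The synopsis list and 3.2 could describe separate measures, and the synopsis study description agrees with 3.2. Someone who attends only follow-up visits is also not clearly adherent to treatment visits. What remains is an unresolved definition and tier.
- **The size is not anchored.** Correct. No document figure supports a 15% or 25% loss after randomisation, and most of the expected 25% loss appears to come before it.

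**Conclusion.** The point holds for this endpoint. The section 3.2 scale gives no value to a randomised participant without a monthly injection, such a participant can be in the all-treated set, and membership may differ by arm. Adherence also lacks a single definition and tier.

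The size depends on arm-specific induction loss, which the documents do not give. Under the assumed distributions, leaving out the zeros barely changes the difference if losses are equal (0.225 against 0.21 at 5%). It halves the difference if XRNTX loses 15% and XRBUP 5% (0.225 against 0.45), and hides a near-zero difference if the losses are reversed (0.225 against −0.05).

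A reader might infer from the 15%/5% row that adding 0 improves power. That is not a general result: power is lower at equal losses and in the reversed case. The argument for the change is that the count should reflect the groups as randomised.

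**What to change.** 1. In 1.1 and 3.2, state one definition and one tier: the number of scheduled monthly injections received, with 0 allowed, in all randomised participants by assigned arm. Section 2.2.1 already argues that receipt of an injection is fully verifiable.
2. Report visit attendance separately, as retention.
3. In 2.3.1, 7.2 and 9.3, say that anyone randomised and then excluded in induction or replaced still counts as 0 for this endpoint, even if outside the all-treated set. Say also whether oral naltrexone in induction is study drug for 9.3.
4. Reconcile the number of scheduled monthly injections across 1.1, 4.1, 6.4 and 13.1, so that the maximum of the count is fixed.

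**Cost.** Wording in those sections. No new data are needed: receipt of injections is already used in 9.4.1, and a 0 needs only the randomisation list and the injection record. Mean adherence will be lower, by m × f: under the assumptions above the XRNTX mean of 2.40 becomes 2.28 at 5% loss and 1.80 at 25%. Power for an arm comparison may fall if losses are similar in the two arms.

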9 STATISTICAL CONSIDERATIONS

9.1 Statistical Hypotheses

Overview of primary hypotheses: Our primary response will be a binary indicator of treatment failure on the XRNTX or XRBUP regimen, defined as ≥ 2 weekly UDS positive for opioids, or self-report of ≥ 2 periods of three or more days of opioid use, or refusing XRNTX or XRBUP, or dropping out of study entirely. In hypotheses H1a and H1b, we are examining the effects of small, pre-specified, sets of measures, so our analyses will focus on model fit and prediction, and not on model selection. In hypothesis H1c, we search for best sets of predictors among demographic and clinical-behavioral variables, and over sets of brain/neural measures, so our focus is on model selection and on avoiding overfitting to the available data.

R61 Phase:

Hypothesis H1 (fMRI): For each of the cue reactivity (H1a), response inhibition (H1b), and connectivity (H1c) brain measured, we have a small number of neural responses associated with one or two regions of interest. These variables are continuously distributed, so we will test Hypotheses 1a, 1b and 1c using a repeated measures analysis of variance (rm-anova). The models will include a within-subject factor for Session (PRE vs ON) and a between-subject factor Group (XRNTX vs XRBUP), and their interaction. To accommodate the anticipated non-normal distributions of the response, we will use a generalized estimating equation (GEE) approach, using robust standard errors, using a compound symmetry working correlation structure for the within-subject correlations between the PRE and ON fMRI scans (Diggle PJ et al 2002). We will perform the rm-anova separately for each ROI (mPFC and VS for H1a, IFC for H1b, and VS-rtIFG and VS-mPFC for H1c). The hypotheses will be addressed by the Session by Group interaction, and we will obtain estimates and standard errors of the PRE vs ON change within each of the two groups, along with the size, standard error and significance of the differences between these estimates.

Sample size considerations for sample: The sample size is adequate for application of the GEE methods to obtain robust standard error (Lipsitz et al 1994). For a test of the PRE vs ON effect, our sample yields 80% power for a one-sided test that the ON levels will be Cohen's $d=0.4$ lower than the PRE levels, consistent with a decrease of Cohen's $d=0.5$ observed in our preliminary data and a decrease of Cohen's $d=0.3$ in the Suboxone sample.

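### The sections disagree on the primary endpoint, and the IDEMO task, listed as primary in section 3.2, has no planned scan run, contrast, hypothesis, region model or schedule row

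*Combined protocol and SAP*

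**What the plan says.** **Synopsis (1.1).** The primary endpoint is the Group by Session interaction "in the brain fMRI signal in 4 cognitive domains". The synopsis names these domains as "motivation, response inhibition, emotional controls and awake rest during the fMRI sessions". The secondary endpoints are "Domain-specific cognitive performance, Urine toxicology, Adherence to follow up and treatment visits".

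**Section 3.2, endpoint list.** Two clinical primaries: "percent of the urine drug screen (UDS) tests positive for opioids during the last month of participation" and "The number of study interventions (1,2 or 3) participant adhered to". Then a surrogate, the fMRI response in what the heading calls three domains: Go-NoGo, opioid cues and "Emotional identification (IDemo Task". A fourth item number is blank.

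**Section 3.2, Primary Hypothesis.** Aims 1 and 2 both sit under this label, including the Phase 2 confirmation of the interaction. H1a to H1c cover cue reactivity, Go-NoGo and resting connectivity.

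**Section 9.1.** It opens with "Our primary response will be a binary indicator of treatment failure" and later calls the same composite the primary outcome. Between these statements it names the full-sample interactions as the primary Phase 2 analysis. It also uses one label twice. The overview says "In hypothesis H1c, we search for best sets of predictors among demographic and clinical-behavioral variables", while the next paragraphs make H1c the resting-connectivity interaction.

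**Section 9.4.1.** The fMRI difference is the primary hypothesis, but its confirmation in the full sample is listed under secondary hypotheses.

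**IDEMO.** Section 6.1 describes it as a 60-face task lasting 10.5 minutes, with accuracy and reaction time as secondary measures.

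**The concern.** The primary endpoint fixes what the trial will be judged on before the data are seen. Here the region interactions, the composite, the urine-screen percentage and the intervention count can each claim primary status from some section. In an open-label trial that leaves room to choose after the results are known.

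IDEMO is the sharper case. It is listed as primary, but the operational sections schedule no acquisition and the statistical sections provide no confirmatory test. Staff following the scan list would not collect it, and the statistician would have no model to run.

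**Working it through.** **1. Endpoint status, place by place**

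| Place | fMRI effect | Composite | Last-month % positive urine | Intervention count |
|---|---|---|---|---|
| 1.1 | primary, four domains | not named | urine toxicology secondary | adherence secondary |
| 3.2 list | primary, three tasks | not named | primary | primary |
| 3.2 Primary Hypothesis | primary heading, both aims | modelled under H2a | not named | not named |
| 9.1 overview | not named as primary | primary response | not named | not named |
| 9.1 Phase 2 | primary analysis | primary outcome | not named | not named |
| 9.4.1 | difference primary, full-sample confirmation secondary | modelled under H2a, secondary | not named | not named |

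No column keeps one status throughout.

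**2. IDEMO through the operational and analysis sections**

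- Scan list (6.1): resting state, Go-NoGo and opioid cue, plus the anatomical scan. IDEMO is in 0 of 3 fMRI runs.
- Contrasts (section 8, image processing): one for cues and two for Go-NoGo. IDEMO is in 0 of 3.
- Hypotheses H1a to H1c (3.2 and 9.4.1): none.
- Region models (9.1): cue mPFC, cue VS, Go-NoGo IFC, rest VS-rtIFG, rest VS-mPFC. IDEMO is in 0 of 5.
- Schedule of Activities (13.1): no row.
- Whole-brain analysis (section 8): planned for each task, but exploratory. It is the only analysis that could cover the IDEMO signal.

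Listed acquisition time is 5 + 5 + 5.5 + 10.5 = 26 min. With IDEMO it is 26 + 10.5 = 36.5 min, or 39 min if Go-NoGo takes the roughly 8 min given in its task description. The limit is 60 min including positioning, so the limit alone does not explain the omission.

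**3. Clinical primaries.** No model takes the last-month urine percentage or the 1/2/3 intervention count as its outcome. Two analyses in 9.1 overlap with them: the logistic model for the composite, and weekly GEE logistic models for opioid use with Group as a predictor.

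**4. Stated power.** Sections 9.1 (70 per group) and 9.2 (80 per group) both give 81% for a one-sided test at d = 0.42. Neither gives alpha. I assume 0.05 and take d as the standardised group difference in change.

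Normal approximation: power = Φ(d√(n/2) − 1.645).

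- n = 70: Φ(0.42 × √35 − 1.645) = Φ(2.485 − 1.645) = 0.800 (noncentral t: 0.796)
- n = 80: Φ(0.42 × √40 − 1.645) = Φ(2.656 − 1.645) = 0.844 (noncentral t: 0.841)

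The 70-per-group figure is reproduced to about one point; the 80-per-group figure is not. At one-sided 0.025 the normal approximation gives 70.0% and 75.7%, so that alpha reproduces neither.

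**5. Lower-grade point: rule for the five region tests.** They are run separately, with no alpha or success rule. The 0.05 and 0.025 in 9.1 belong to the logistic models, and two of three domains is the Phase 1 milestone. Aim 2 refers to all domains without saying whether one or both regions count where a domain has two. If one suffices, the chance of a false positive in a null two-region domain is 1 − 0.95² = 9.75% with independent regions at 0.05 each. At 0.025 each it is 1 − 0.975² = 4.9%.

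**The case against.** **The plan is mostly coherent.** The synopsis, the Primary Hypothesis in 3.2, the Phase 2 primary analysis in 9.1, the primary hypothesis in 9.4.1 and the power statement in 9.2 all favour the fMRI interaction. The secondary heading in 9.4.1 is the outlier. The composite in the Phase 2 text could be just the dependent variable of a second analysis. Much of this stands: a reader might infer that nobody can tell what decides the trial, and that goes too far. But the 9.1 overview calls the composite the primary response outright, and 3.2 lists clinical endpoints as primary that the synopsis makes secondary.

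**Broken layout.** The synopsis labels are displaced. Someone might read each label as preceding its text, which would make cognitive performance, urine toxicology and adherence primary. That leaves the secondary-endpoint label empty and the interaction sentence unlabelled, so it is not tenable. The blank fourth item in 3.2 may be lost text, so the absence of resting state there is weak evidence. The conflict does not depend on either.

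**IDEMO may have been dropped or be exploratory.** Section 3.1 says some Phase 1 probes may not survive into Phase 2. But no text says IDEMO was dropped, and the Phase 1 models already omit it. The task is not wholly unspecified, given the description in 6.1. Section 10.2 says affect regulation is not included, but whether that means this task is unclear.

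**Clinical outcomes are analysed.** This is partly right: the composite and the weekly models bear on them, though not as 3.2 defines them.

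**Conclusion.** The inconsistency is real and must be fixed. Four candidate endpoints carry primary status somewhere, H1c names two hypotheses, and a listed primary task appears in 0 of 3 fMRI runs, 0 of 3 contrasts and 0 of 5 region models. This rests on the text alone, so confidence is high. It is a contradiction in labelling and coverage, not an absence of any discernible primary aim.

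The power mismatch is firm if alpha is one-sided 0.05: about 80% at 70 per group and 84% at 80.

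The missing rule for the five region tests is a lower-grade point. A reader might infer that the plan has a known joint power or a known inflated error rate. The documents do not support that. With d = 0.42 in all five regions, 70 per group and correlation 0 to 0.5, power for all five is 32–51%. The plan gives effects only for VS (0.38) and mOFC (0.42), and mOFC is not among the five regions. With the cue regions at 0.42 and 0.38, setting the other three to 0.2 gives 2–11%, and setting them to 0.5 gives 43–58%. An error rate of 17–23% would arise only if any single region sufficed, which no section says.

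**What to change.** - **One endpoint list** in 1.1, 3.2, 9.1 and 9.4.1, with the sponsor choosing the primary. The five modelled region interactions fit Aim 2, the Phase 2 primary analysis and the power statements in 9.1 and 9.2. Section 9.1 also powers the composite analysis (odds ratio 1.75 or 1.86), so that choice is open too. The change is wording, but some endpoints lose primary status.
- **Composite, last-month urine percentage and intervention count:** label each as secondary, or give it a model that matches its definition.
- **H1c:** use the label for one hypothesis only.
- **IDEMO:** make it exploratory, which is wording only, or add it to the scan list, schedule, contrasts, hypotheses and region models. Adding it costs 10.5 min per session. Over two sessions that is 140 × 2 × 10.5 / 60 = 49 scanner hours for 140 participants. For 200 it is 70 hours, an upper bound: scanning follows detoxification, and section 5.3 expects only 160 to reach the first monthly injection (56 hours, before later dropout).
- **Power:** state alpha and one sample size per group, and recompute the 81%.
- **Region rule (lower grade):** state the per-test alpha and whether a two-region domain needs one or both. If one suffices, adjust within that domain, for example 0.025 each. With d = 0.42 throughout and 70 per group, this lowers one-region-per-domain power from about 73% to 65–66%. If all five are required, state joint power with its effect-size and correlation assumptions.
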